2.3.6. Starting dose rationale & administration schedule

In the study CL1-64315-001 assessing S64315 as a single agent in a weekly schedule without lead-in dose period, doses from 50 to 500 mg were tested. Based on all the DLT data collected since the beginning of the study across 38 evaluable patients with AML or MDS, 500 mg was identified to be a toxic dose and 300 mg was the highest dose considered safe by the statistical model i.e. BLRM with EWOC criterion. Nevertheless, considering the global safety observed at 300 mg (except DLT), it was decided not to overpass S64315 weekly dose of 250 mg.

- Arm A evaluating the combination of S64315 with azacitidine in the frame of a phase I/II trial

• Dose escalation phase I part

The choice of the starting dose of S64315 in the Arm A is based on the first clinical data (safety and PK profile) from the administration schedule assessing weekly S64315 as a single agent, taking into account the anticipated activity, the limited DDI risk between S64315 and azacitidine and the potential risk of overlapping toxicity regarding the haematotoxicity and GI toxicity. Thus, following a conservative approach, the started dose of S64315 proposed to assess the combination of S64315 and azacitidine will be 50 mg once a week as full tested dose. The dose escalation will be preceded by a 2-week lead-in dose (LID) period of weekly S64315 at a fixed dose of 25 mg for LID1 and 50 mg for LID2.

The introduction of the LID period with fixed low doses of S64315 aims:

- to allow an early detection of patients with cardiac sensitivity to S64315 and to prevent subsequent administrations with higher doses to these patients
- to improve the overall tolerance to S64315
- to reduce the risk of tumour lysis syndrome (TLS)
- Azacitidine will be administered via subcutaneous injection at the dose of 75 mg/m², daily from day 1 to day 7, followed by a rest period of 21 days (28-day cycles), according to the current E.U SmPC.

With regards to the administration schedule of the combination, there is an interest to administer azacitidine before the targeted dose of S64315 in order to sensitize the tumour cells to S64315 (Caenepell, 2018). For this reason, the administration schedule starting from cycle 1 onwards, over 28-day cycles is, as follows:

- Azacitidine daily administered via a subcutaneous injection, from day 1 to day 7 (D1 to D7), followed by a rest period of 21 days

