The study start is defined as the date of the first visit of the first patient, corresponding to ICF signature. It will be divided into the following periods for each patient of Arm A.

Screening visit

The screening eligibility criteria will be checked after the patient informed consent is obtained.

Inclusion period

The inclusion and exclusion criteria will be checked. The inclusion period can last up to 15 days before starting the LID period. The patient is included when he/she has met all the inclusion criteria.

S64315 lead-in dose period

The lead-in dose period will last 2 weeks. S64315 LID1 will be administered on D-13 at 25 mg and LID2 on D-6 at 50 mg. LID1 and LID2 doses will be fixed all along the study.

Combination treatment period

A treatment cycle will consist of 28 days for patients treated with S64315 in combination with azacitidine during the dose escalation phase I part:

- Weekly schedule for S64315 on CxD2, CxD9, CxD16 and CxD23
- Daily schedule for azacitidine from CxD1 to CxD7 followed by a 21-day rest period

The administration schedule for the expansion phase II part will be defined according to what is observed during the dose escalation phase I part.

The planned duration of combination treatment is until disease progression, unacceptable toxicity, treatment failure (defined as failure to achieve CR, CRi, PR, or MLFS after at least 6 cycles of study treatment) or patient/physician decision. In case of myelosuppression within the context of non-active AML, a 4-week interruption of administration of one or both IMP(s) will be allowed for bone marrow recovery at the investigator's discretion after discussion and approval from the Sponsor.

If the patient is benefiting from the study treatment according to the investigator's judgement and if it is in the patient's best interest to continue the combination of S64315 with azacitidine, the patient may remain on study treatment. In case the patient becomes eligible for transplant, patient's treatment discontinuation should be left at the investigator's decision.

Withdrawal visit (WV): up to 28 days after the last dose of IMP

Post-withdrawal follow-up

After the withdrawal visit, a contact or telephone call will be done for the patients:

- every 3 months (± 15 days) from the WV and up to 6 months, except in case of consent withdrawal for the dose escalation phase I part

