4.1.3.2. Dose administration schedules

The initial schedule will consist of a 2-week S64315 lead-in dose period followed by a 28-day cycle with the combination, i.e. a weekly regimen for S64315 and a daily regimen for azacitidine over 7 days.

Alternative dosing schedules based on the observed clinical safety, PK/PD data and non-clinical data (in vitro, in vivo, PK/PD modelling data) may be further explored. They should be integrated in the protocol via an amendment.

S64315 will be administered via intravenous (IV) infusion over at least 2h once every week, as follows:

- **2-week lead-in dose period** i.e. fixed lead-in dose 1 (LID1) of 25 mg on D-13 and fixed lead-in dose 2 (LID2) of 50 mg on D-6
- followed by the **combination treatment period over 28-day cycles**, i.e. on CxD2, CxD9, CxD16 and CxD23

The starting dose will be 50 mg. A panel of dose from 25 mg (-1) and up to 250 mg could be explored according to the dose escalation process of the BLRM. For more details, please refer to [Table \(4.1.3.3\) 1](#).

A minimum of 5 days between two infusions of S64315 is required.

An infusion could be postponed in case of 1-day delay and should be discussed with the Sponsor in case of 2-day delay, for any reason other than medical / toxicity.

Azacitidine will be administered during the combination treatment period at 75 mg/m² via subcutaneous (SC) injection, daily for 7 days, i.e. from CxD1 to CxD7, followed by a rest period of 21 days (28-day cycle).

On days of concomitant administration of S64315 and azacitidine (CxD2), azacitidine should be administered 2h (\pm 10 min) prior to S64315.

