If the patient is benefiting from the study treatment according to the investigator's judgement and if it is in the patient's best interest to continue the combination of S64315 with azacitidine, the patient may remain on study treatment. A patient must discontinue the combination if the toxicity recurs with the same or worse severity after resumption of dosing, unless the investigator decides it is in the patient's best interest to continue the combination of IMPs and upon documented agreement with the Sponsor.

If one IMP is permanently discontinued, both drugs should be permanently discontinued. A patient must be withdrawn from the study if one the IMPs is interrupted for more than 28 consecutive days from C1D2, for any reason. However, for patients with LVEF decline, IMP interruptions of up to 35 consecutive days are permitted.

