6.1.2. Administration/re-administration criteria

- Criteria to fulfil before each S64315 infusion
 - Before each S64315 infusion, biological parameters should be checked in order to detect any toxicity (see [Table \(8.12\) 1](#))
 - Patients with Grade ≥ 2 hypo/hypercalcemia and/or hypo/hypermagnesia and/or hypo/hyperkalaemia despite attempts at medical correction should not be treated with S64315
 - Patients with WBC ≥ 10 G/L despite attempts at medical correction should not be treated with S64315. Hydroxycarbamide can be used to reduce the circulating blast count before and throughout the treatment period
 - AST and ALT ≤ 3 x ULN (except for LID1: AST and ALT ≤ 1.5 x ULN)
 - Total bilirubin level ≤ 1.5 x ULN, except for patients with known Gilbert's syndrome, who are excluded if total bilirubin > 3.0 x ULN or direct bilirubin > 1.5 x ULN
 - In the case of an S64315 interruption ≥ 28 days, its readministration must be preceded by a lead-in dose period (except for patients in CR/CRi) which is called additional Lead-In dose period. See [Table \(4.1.2\) 1](#) for more details on safety assessments required.
- Criteria to fulfil before each first azacitidine administration (i.e. CxD1)

Patients should be monitored for haematological toxicity and renal toxicities. A delay in starting the next cycle or a dose adjustment due to haematological toxicity and/or renal toxicity may be necessary according to E.U. SmPC (see [Table \(8.12\) 2](#)). WBC, absolute neutrophil count (ANC), platelets, serum creatinine, BUN and serum bicarbonate will be assessed before starting the next treatment cycle.

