8.12. Management of treatment dose adaptations due to toxicities

For patients who do not tolerate the protocol-specified dosing schedule, dose interruptions and/or reductions are either recommended or mandated in order to allow patients to continue the study treatments.

Dose modifications recommendations for S64315 are summarised in [Table \(8.12\) 1](#).

A patient must discontinue treatment with S64315 if, after treatment is resumed at a lower dose, the toxicity recurs with the same or worse severity, unless in the opinion of the investigator it is in the patient's best interest to continue S64315, and upon documented agreement with the Sponsor.

For each patient, once a dose reduction has occurred, the dose may not be re-escalated during the subsequent cycles unless in the opinion of the investigator it is in the patient's best interest to continue S64315, and upon documented agreement with the Sponsor.

When a patient meets the criteria for S64315 discontinuation described in the table, he/she must discontinue both IMPs.

Dose modifications for azacitidine must be done according to azacitidine E.U. SmPC (see [Table \(8.12\) 2](#)).

These dose changes must be recorded in the eCRF.

Table (8.12) 1 - Criteria for interruption and re-initiation of S64315

Recommended dose modifications for S64315	
Worst toxicity CTCAE Grade^a (unless otherwise specified)	During a cycle of therapy
Investigations (Renal)	
Serum creatinine	
Grade 2 (> 1.5 – 3 x ULN or > 1.5 – 3 x baseline)	Omit dose until resolved to Grade ≤ 1 or baseline, then: - If resolved in ≤ 14 days, then maintain dose level - If resolved in > 14 days, then ↓ 1 dose level
Grade 3 (> 3 – 6 x ULN or > 3 x baseline)	Omit dose until resolved to Grade ≤ 1 or baseline, then ↓ 1 dose level
Grade 4 (> 6 x ULN)	Discontinue patient from test drug treatment
Note: If intercurrent illness, e.g. dehydration due to diarrhoea or febrile infections, leads to prerenal insufficiency, this should not be considered drug related and the criterion for dose modification not fulfilled	
Investigations (Hepatic)	
Isolated Total Bilirubin elevation^b	
Grade 2 (> 1.5 - 3.0 x ULN if baseline was normal, >1.5 - 3.0 x baseline if baseline was abnormal)*	Omit dose until resolved to Grade ≤ 1, then: - If resolved in ≤ 14 days, maintain dose - If resolved in > 14 days, ↓ 1 dose level

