Grade 2	Maintain dose level but initiate/intensify appropriate skin toxicity therapy (e.g. antihistamines, topical corticosteroids and low-dose systemic corticosteroids) as per local institutional guidelines and monitor closely Consider skin biopsy for evaluation
Grade 3, despite skin toxicity therapy	Omit dose and reassess the patient weekly until resolved to Grade \leq 1, then: 
 - If resolved in \leq 14 days, \downarrow 1 dose level - If resolved in $>$ 14 days, discontinue patient form test drug treatment Consider referral to dermatologist and manage rash per dermatologist's recommendations Consider skin biopsy for evaluation

Grade 4, despite skin toxicity therapy	Discontinue patient from study treatment Consider referral to dermatologist and manage rash per dermatologist's recommendations Consider skin biopsy for evaluation
Cardiac disorders	
QTcF Prolongation	
QTcF interval \geq 481ms or increase of $>$ 60 ms from baseline on at least two separate ECG	Omit S64315 dose, correct the possible electrolytes abnormalities (e.g. potassium, magnesium, etc.) and perform frequent ECGs* until resolves to Grade \leq 1, then: 
 - If resolved in \leq 14 days, \downarrow 1 dose level. Triplicate ECGs must be monitored on D1 of each cycle throughout the study - If resolved in $>$ 14 days, discontinue patient from test drug treatment *Perform at least weekly ECGs until 2 weeks following resolution of the QTc prolongation
LVEF Decrease	
Asymptomatic, absolute decrease in LVEF of 10% or greater from baseline and LVEF $<$ 50%	Omit dose, obtain consultation with a cardiologist, and repeat cardiac imaging after 4 weeks 
 - If improved to \leq 10% from baseline and \geq 50% within 4 weeks, then \downarrow 1 dose level. Monitor LVEF on D1 of each subsequent cycle for at least 3 cycles; if no recurrence of LVEF decline and if agreed by the cardiologist, the frequency may then be decreased to every other cycle. - If not improved to \leq 10% from baseline and \geq 50% within 4 weeks, then discontinue patient from test drug treatment
Absolute decrease in LVEF of 20% or greater from baseline and LVEF $<$ 40% OR Symptomatic congestive heart failure	Discontinue patient from test drug treatment and obtain consultation with a cardiologist

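### The S64315 lead-in is fixed at 25 mg then 50 mg with no cap at the assigned dose, so a patient reduced to 25 mg can be given 50 mg on restart

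*Protocol*

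**What the plan says.** - **Lead-in doses.** Protocol 4.1.3.2 specifies a "fixed lead-in dose 1 (LID1) of 25 mg on D-13 and fixed lead-in dose 2 (LID2) of 50 mg on D-6". Section 4.1.1 adds that "LID1 and LID2 doses will be fixed all along the study".
- **Purpose.** Section 2.3.6 gives three aims. The first is "to allow an early detection of patients with cardiac sensitivity to S64315 and to prevent subsequent administrations with higher doses to these patients". The others are better overall tolerance and a lower risk of tumour lysis syndrome.
- **Repeat lead-in.** Under 6.1.2, after an S64315 interruption of 28 days or more, "its readministration must be preceded by a lead-in dose period (except for patients in CR/CRi) which is called additional Lead-In dose period". No doses are restated there. The only change noted for it, in a footnote to Table (4.1.2) 1, is that PK and PD sampling is dropped.
- **LVEF decline.** For an asymptomatic absolute fall of at least 10% to below 50%, Table (8.12) 1 says "Omit dose, obtain consultation with a cardiologist, and repeat cardiac imaging after 4 weeks". On recovery, S64315 resumes one dose level lower.
- **Length of interruption.** Section 5.8.1 withdraws a patient if either product is "interrupted for more than 28 consecutive days from C1D2, for any reason", but "for patients with LVEF decline, IMP interruptions of up to 35 consecutive days are permitted".
- **Dose levels.** Table (4.1.3.3) 1 puts 25 mg (level -1) directly below the 50 mg starting dose and allows no reduction below it.
- **Re-escalation.** Section 8.12 (and the Synopsis) says that "once a dose reduction has occurred, the dose may not be re-escalated during the subsequent cycles", unless the investigator judges it in the patient's interest and the sponsor's agreement is documented.

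**The concern.** Each rule is sensible alone. Together they can give a patient whose dose was halved for toxicity one more infusion at the higher dose, through a mandatory step and not a clinical decision. In the cardiac case this runs against the first stated aim of the lead-in: the procedure meant to keep higher doses from cardiac-sensitive patients would deliver one. The stake is patient safety. It does not bear on the efficacy design or on the dose-escalation model's operating characteristics.

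**Working it through.** **1. Dose after reduction.** From 50 mg, one level down is 25 mg, which is the floor.

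**2. Is the repeat lead-in reached after LVEF decline?** Assume the D23 infusion was given on schedule, the decline is found at the scheduled echocardiogram (on D1 or up to 2 days before, section 8.2.2), and imaging is repeated 28 days later. In a 28-day cycle the next D1 is 6 days after D23 and the next D2, the first missed infusion, is 7 days after. Section 6.1.2 does not say from which day an interruption is counted, so both counts are shown. One DLT criterion in Table (4.1.3.5) 1 counts from the first missed dose.

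| Echo before D1 | Re-imaging, from last infusion | Permitted restart days to 35 | Re-imaging, from first missed dose | Permitted restart days to 35 | Of these, day 28 or later |
|---|---|---|---|---|---|
| 0 days | 6 + 28 = 34 | 34-35 (2) | 34 - 7 = 27 | 27-35 (9) | 8 |
| 1 day | 5 + 28 = 33 | 33-35 (3) | 33 - 7 = 26 | 26-35 (10) | 8 |
| 2 days | 4 + 28 = 32 | 32-35 (4) | 32 - 7 = 25 | 25-35 (11) | 8 |

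Counted from the last infusion, every permitted restart requires the lead-in. Counted from the first missed dose, it is avoided only by restarting by day 27, which is 0 to 2 days after re-imaging. For a decline found at an unscheduled echo 0 to 6 days after an infusion, re-imaging falls at day 28-34 or day 21-27 on the two counts. So the route is reachable on either count.

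**3. What is given.** Not in CR/CRi, restarting at day 28 to 35:

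- As written: 25 + 50 + 4 x 25 = 175 mg over the lead-in and first restarted cycle.
- Capped at the assigned dose: 25 + 25 + 4 x 25 = 150 mg.
- Difference 25 mg; ratio 175/150 = 1.167.
- The second lead-in dose is 50/25 = 2 times the assigned dose and equals the dose on which LVEF fell.

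**4. Prolonged cytopenia.** In Table (8.12) 1, a patient with cleared marrow and grade 4 neutropenia and thrombocytopenia resolving after more than 28 days may continue at a lower dose after discussion with the sponsor. From 50 mg this gives the same sequence, provided that row is taken to prevail over the 28-day limit in 5.8.1 and the patient is not in CR/CRi (for example, in MLFS only).

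**5. Level -1 cohort.** Section 4.1.3.3 allows a 25 mg cohort if 50 mg is not well tolerated. With fixed lead-in doses, its patients would receive 50 mg on D-6 and 25 mg weekly from C1D2.

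**6. Does another rule prevent it?** The re-escalation rule is the only candidate. It speaks of subsequent cycles, whereas 4.1.1 treats the lead-in and the cycles as separate periods. It allows an override and does not mention the repeat lead-in. Section 6.1.2 does not refer to it. A site must choose between the two.

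**The case against.** **The rules can be read together benignly.** The re-escalation rule is written for reduced patients. The SAP treats the lead-in as a cycle when computing dose intensity (3.2.5.1 and 4.2.1.5), so subsequent cycles could include it. The fixed-dose statement could mean only that the lead-in does not change between cohorts. The registration form (Appendix 2) leaves both lead-in doses for the sponsor to fill in. All this stands as a reason not to call the text contradictory. It does not supply a cap: the SAP is an analysis document, and nothing tells a site to use other doses.

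**The risk is contained.** Restart after LVEF decline requires LVEF at or above 50% and back within 10% of baseline. Patients are hospitalised around each lead-in infusion, with cardiac markers to 72 h and ECGs to 24 h, and a troponin rise leads to dose omission. The next LVEF check, on D1, comes about 6 days after the second lead-in dose and before further S64315. This stands, although no echocardiogram is listed within the lead-in, so that check follows the 50 mg infusion.

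**50 mg alone may be milder than 25 mg with azacitidine.** In Appendix 8 the prior mean DLT rate is 0.108 for 50 mg S64315 alone and 0.156 for 25 mg in combination. This weakens the level -1 cohort case. It says little about a patient who has already shown toxicity at 50 mg.

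**Two stronger readings are not supported.**

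- A reader might infer that LVEF decline is the main use of the repeat lead-in, because 5.8.1 withdraws other patients after 28 days. But 4.1.1 allows a 4-week hold for myelosuppression, Table (8.12) 1 allows continuation after longer cytopenia, and the lead-in also serves tolerance and tumour lysis.
- A reader might infer that the DLT tables are wrong, because 10.2.6 models a lead-in DLT as monotherapy while Protocol 10.4.4.2 and SAP 2.1 and 3.4 place it under the planned dose level. The endpoint explicitly starts at the lead-in, tabulation by planned dose is a declared descriptive convention, and SAP 3.4.1 provides patient listings. That is a presentation choice.

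**Conclusion.** The point holds as a missing exception in a dosing rule. Followed literally, the protocol gives one 50 mg infusion, twice the assigned dose, to a patient reduced from 50 to 25 mg who is not in CR/CRi and restarts after 28 days or more. A level -1 cohort would also receive 50 mg as its second lead-in dose. The excess is a single 25 mg increment per lead-in.

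This assumes that the fixed doses apply to the repeat lead-in, which is the natural reading because no others are given. The documents do not say how many patients meet the conditions or whether a 25 mg cohort was opened. The number is probably small: SAP 1.3 and 1.3.1 say that escalation has stopped and that neither the expansion nor Arm B will be conducted. The documents do not show that any patient was dosed this way or harmed. The change is still worth making for any patient remaining on treatment and for any later use of this schedule.

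**What to change.** In Protocol 4.1.1, 4.1.3.2 and 6.1.2 add: *No lead-in or repeat lead-in infusion may exceed the patient's currently assigned S64315 dose (25 mg / 25 mg when that dose is 25 mg).*

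Amend 10.2.6, which now ties a LID2 DLT to 50 mg monotherapy, so that a lead-in DLT is attributed to the S64315 dose actually given. While 6.1.2 is open, state the day from which an interruption is counted. In the DLT table, at most add a footnote giving the dose actually received for any lead-in DLT.

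The cost is a few sentences, with no extra patients, visits or procedures. The one loss is the 25-to-50 mg step for patients who will not be treated above 25 mg.

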4.1.2. Investigation schedule

Table (4.1.2) 1 describes the efficacy, safety and other assessments performed during the dose escalation phase I part of the study for **Arm A**.

Investigation schedule for the expansion phase II part for **sub-arms A1 and A2** will be further defined according to what is observed during the dose escalation phase I part.

Investigation schedule for **Arm B** will further defined according to the results of Arm A.

	Protocol section	Screening visit	Inclusion period	S64315 Lead-in dose period		Cycle 1					Cycle 2 and cycle 3					Cycle 4 and beyond					In case of suspected progression	W V	F U			
				D-13	D-6	D1	D2	D9 ^a	D16	D23	D1	D2	D9	D16	D23	D1	D2	D9	D16	D23						
Height	8		X																							
Body weight	8		X			X AZA predose					X AZA predose					X AZA predose									X	
DLT assessment	4 1 3 6			X during LID period and cycle 1										X (DLT monitoring)												
Adverse events	8 3		X	X	X	X	X	X	X	X	X	X	X	X	X	X	X	X	X	X	X	X	X	X	X	X
Laboratory examinations																										
Blood haematology	8		X ^C	X ^D Predose*, 24h and 48h after EoI	X ^D predose*, 24h and 48h after EoI	X AZA predose*	X S64315 predose* and EoI	X S64315 predose*	X S64315 predose*	X ^P S64315 predose*	X AZA predose*	X S64315 predose*	X S64315 predose*	X S64315 predose*	X S64315 predose*	X AZA predose*	X S64315 predose*	X S64315 predose*	X S64315 predose*	X S64315 predose*	X S64315 predose*				X	
Blood biochemistry (fasted when applicable ^k)	8		X ^C	X Predose*, 8h ^a , 24h and 48h after EoI	X Predose*, 8h ^a , 24h and 48h after EoI	X AZA predose*	X S64315 predose* EoI, 8h ^a , 24h ^a and 72h ^a after EoI ^b	X S64315 predose* 24h after EoI ^b	X S64315 predose*	X S64315 predose*	X Aza predose*	X S64315 predose*	X S64315 predose*	X S64315 predose*	X S64315 predose*	X Aza predose*	X S64315 predose*	X S64315 predose*	X S64315 predose*	X S64315 predose*	X S64315 predose*				X	
Cardiac markers (troponin, CPK-MB and BNP)	8		X ^{CJ}	X Predose*, 6h, 24h, 48h and 72h after EoI	X Predose*, 6h, 24h, 48h and 72h after EoI	X AZA predose*	X S64315 predose*, 6h, 24h, 48h and 72h after EoI	X S64315 predose*, 6h, 24h, 48 and 72h after EoI	X ^E S64315 predose*	X ^E S64315 predose*	X Aza predose*	X ^E S64315 predose*	X ^E S64315 predose*	X ^E S64315 predose*	X ^E S64315 predose*	X Aza predose	X ^E S64315 predose*	X ^E S64315 predose*	X ^E S64315 predose*	X ^E S64315 predose*						
TLS monitoring - laboratory parameters (haematology & biochemistry)	8 2 8			X Predose*, 2h, 4h, 8h, 24h,	X Predose*, 2h, 4h, 8h, 24h,	X AZA predose, 1h30, 6h post injection	X S64315 predose*, 2h, 4h, 8h and 24h after S64315 EoI	X S64315 predose*, 2h, 4h, 8h and 24h after S64315 EoI	X ^F	X ^F		X ^F	X ^F	X ^F	X ^F		X ^F	X ^F	X ^F	X ^F						
Blood coagulation	8		X ^C	X Predose*		X AZA predose*					X AZA predose*					X AZA predose*									X	
Thyroid function	8		X ^C	X Predose*		X AZA predose*					X AZA predose*					X AZA predose* until C6, then every 4 cycles										
Hepatitis markers	8		X ^C																							
Urinary analysis	8		X ^C	X Predose*		X AZA predose*					X AZA predose*					X AZA predose*									X	
Pregnancy test	8		X ^C Serum								X serum or urine					X serum or urine									X serum	

	Proto col section	Scree ning visit	Inclusi on period	S64315 Lead-in dose period		Cycle 1					Cycle 2 and cycle 3					Cycle 4 and beyond					In case of suspected progression	W V	F U				
				D-13	D-6	D1	D2	D9 ¹	D16	D23	D1	D2	D9	D16	D23	D1	D2	D9	D16	D23							
Chest X-Ray	8 2 1		X																								
ECG (triplicate) ^G	8		X ^C	X predose, EoI, 1h, 2h, 6h, 24h after EoI	X predose, EoI, 1h, 2h, 6h, 24h after EoI	X AZA predose	X S64315 predose, EoI, 1h, 2h, 6h, 24h after EoI	X S64315 predose, EoI, 1h, 2h, 6h, 24h after EoI	X S64315 predose, EoI	X S64315 predose, EoI		X S64315 predose, EoI															X
ECHO/MUG A scan	8		X ^C									X Aza predose															X
Pharmacokinetic measurements **																											
Blood samples ^H	9 2 1			X EoI, 4h and 24h after EoI			X S64315 predose, 10, 30 after SoI, EoI, 30, 1h, 2h, 4h, 7h =1h after EoI +D3: S64315 24h after EoI																				
Pharmacodynamics measurements **																											
BMB	9 3		X																								X
Blood samples (protein expression)	9 3			X predose		X AZA predose	X AZA predose, S64315 predose, 1h and 24h =2h after EoI					X AZA predose	X AZA predose, S64315 predose, 1h and 24h =2h after EoI														X
Blood samples (genomic alterations and MRD)	9 3			X predose		X AZA predose								X C2D1 and C3D1 AZA predose and anytime in case of CR when CR achieved and every 3 months during study treatment period													X

	Protocol section	Screening visit	Inclusion period	S64315 Lead-in dose period		Cycle 1					Cycle 2 and cycle 3					Cycle 4 and beyond					In case of suspected progression	W V	F U				
				D-13	D-6	D1	D2	D9 ¹	D16	D23	D1	D2	D9	D16	D23	D1	D2	D9	D16	D23							
Absolute total and B lymphocyte count	93			X _{predose}		X _{AZA predose}	X _{AZA predose, S64315 predose, 4h, 6h, 24h and 72h after EoI}	X _{predose 24h after EoI}	X _{predose}		X _{AZA predose}			X _{predose}		X _{AZA predose}			X _{predose}								
BMA (protein expression)	93		X								X in case of response, at least PR								X								
BMA (genomic alterations and MRD)	93		X								X C2D1 and C3D1 AZA predose and anytime in case of CR when CR achieved and every 3 months during study treatment period					Anytime in case of CR when CR achieved and every 3 months during study treatment period								X			
Saliva (DNA sequencing)	93		X								X in case of CR																
Copy of karyotype report (if available)	93		X																					X			
Pharmacogenomics measurements (optional)																											
PG measurements	94					X _{AZA predose}																					
IMP circuit																											
S64315 dispensation / administration / compliance ¹	611			X	X		X	X	X			X	X	X	X			X	X	X	X						
Azacitidine dispensation / administration / compliance ¹	611					X Daily from D1 to D7					X Daily from D1 to D7					X Daily from D1 to D7											

SoI: start of infusion

EoI: end of infusion

AZA: azacitidine

A: (Efficacy measurements) Predose exams to be performed within 24h prior to C1D1; ideally in the morning on C1D2 and C1D3 and within 3 days prior to C2D1 and C3D1

B: (Efficacy measurements) BMA and BMB predose to be performed within 2 days prior to C2D1 and within 7 days prior to C3D1 and C7D1

C: (Safety measurements) Exams to be performed within 7 days prior to inclusion and results available for inclusion

D: (Safety measurements) WBC count must be checked twice a week during the LID period in order to maintain this level < 10 G/L

E: (Safety measurements) In case of any troponin increase observed after any of the two first infusions of cycle 1, it will be recommended to assess cardiac markers at 48h and 72h after S64315 EoI and after each subsequent infusion (before discharge and beyond, if needed), on a regular basis

F: (Safety measurements) Applicable for all patients with a risk of developing TLS according to the investigator's judgment: prior to each S64315 infusion (predose) and 2h, 4h, 8h and 24h±2h after each S64315 EoI

G: (Safety measurements) ECG predose could be performed within 24 hours before any S64315 infusion or after azacitidine before S64315 CXD2 infusion

H: (Pharmacokinetic measurements) PK predose time points should be collected 5-30 minutes before infusion/injection; PK S64315 EoI time points should be collected within 5 to 10 minutes before the end of infusion

I: (IMP circuit) On days of concomitant administration of S64315 and azacitidine (CxD2), azacitidine should be administered 2 hours (±10 minutes) prior to S64315

J: Except CPK-MB and BNP

K: (Biochemistry) Assessments should be limited to AST, ALT and total bilirubin for 8h timepoints after LID1 and LID2 EoI, 8h, 24h and 72h timepoint after C1D2 EoI and 24h timepoint after C1D9 EoI. Fasting conditions are not required for these timepoints.

L: If Day 9 administration is not performed, all scheduled assessments should be performed at the next S64315 infusion (2nd S64315 infusion in cycle 1).

*: Predose laboratory examinations to be performed within 3 days prior to LID1 or LID2, within 24h prior to S64315 C1D2 and within 3 days prior to any other IMP administration

** : In case of an additional lead-in dose period (see [section 6.1.2](#)), all investigations must be performed except those for Pharmacokinetic and Pharmacodynamics measurements.

Table (4.1.2) 2 - Pharmacokinetic measurements for arm A

	Protocol section	Lead-in dose period	D1	D2	D3	D9	D10
S64315 blood samples	9.2.1	LID1 EoI**, 4h and 24h after LID1 EoI**	NA	Predose*, 10' and 30' after SoI, EoI**, 30', 1h, 2h, 4h and 7h ± 1h after EoI**	24h after EoI**	NA	NA

AZA: azacitidine; LID1: Lead-in dose 1; SoI: Start of infusion; EoI: End of Infusion; NA: not applicable

*PK predose time points should be collected 5-30 minutes before infusion/injection

**PK S64315 EoI timepoints should be collected within 5 to 10 minutes before the end of infusion

For further practical details, methods of measurement are provided in [sections 7, 8 and 9](#).

The maximum total volume of blood collected per patient during the study will be around 918 mL until Cycle 3, around 180 mL per additional cycle, around 30 mL in case of suspicion of disease progression and around 20 mL in case of withdrawal visit.

